## 8. CORRELATIVE STUDIES

### 8.1. Biologic activity:

Assessing the biologic activity of IRX5183 in AML and MDS patients is critical to the interpretation of any clinical activity. Successful induction of terminal differentiation would be expected to be measurable by changes in the malignant cell phenotype as well as possible cytogenetic changes. The following biologic correlatives will be conducted in the laboratories of Drs. [name] and [name]:

1. ***In vivo* induction of terminal differentiation** - PB and BM markers of myeloid differentiation such as CD15 and CD11b (as directed by disease phenotype) will be measured by flow cytometry prior to the initiation of therapy and repeated on the day 14 ( $\pm$  3) and/or post cycle 1 specimens, with a preference for day 14 ( $\pm$  3), while ongoing differentiation is more likely.
2. **Effect on leukemia stem cells as an indicator of differentiation** – ratio of LSC population to normal HSC population will be determined at baseline, day 14 ( $\pm$  3 days), and later endpoints in select patients. If the patient's leukemia consists of an ALDH intermediate population, we will determine the ratio of CD34+CD38ALDHint LSCs to

CD34+CD38ALDHhigh normal HSCs. We will use techniques as we have previously published (Gerber et al., 2012).

3. ***In vivo* changes in measurable cytogenetic alterations** – baseline clinical fluorescent in situ hybridization (FISH) analysis will be done prior to starting treatment and subsequent analyses will take place with each clinical BM, in order to assess for a cytogenetic response to therapy. When possible, FISH will additionally be used to quantify the cytogenetic changes in PB and marrow myeloid progenitors prior and following therapy on day 14 ( $\pm$  3 days) and/or after cycle 1. The presence of mature neutrophils with the malignant cytogenetic abnormality in the PB will serve as evidence for terminal differentiation of leukemia cells from the therapy.
4. ***In vitro* induction of terminal differentiation** – the susceptibility of malignant progenitors to IRX5183 will be studied *in vitro*. CD34 positive progenitors will be isolated from bone marrow or PB and exposed to IRX5183 in the presence and absence of the patient's own stromal feeder layer. We will look at the impact on differentiation by flow cytometry using various differentiation markers (e.g. CD15, CD11b) and by CFU assay. Techniques will be done as previously reported (Su et al., 2015) and per Laboratory Manual.
5. **Plasma differentiating activity** – the differentiating ability of different dose levels of IRX5183 will be assessed by treating NB4 APL cell lines with patient plasma obtained at day 14 and beyond and then measuring CD11b expression by flow cytometry, compared to control (see Lab Manual).
6. **Cell cycle and apoptosis assays** – cell cycle and apoptosis assays will be performed in CD34+ cells at baseline and different time points throughout the trial. We will assess viable MNCs with flow cytometry, looking at Annexin-5 and Propidium Iodide (PI) as markers of apoptosis and Ki67/Hoechst to assess cells in G0/G1/S/G2M. In addition, we will assess Bcl-2 expression levels by Western blot. See Lab Manual for full details.

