## **2.2. Myelodysplastic syndrome:**

Myelodysplastic syndromes (MDS) are a complex and heterogeneous group of disorders characterized by ineffective hematopoiesis manifest by cytopenias, dysplasia, and increased risk of infection. In the general population the incidence is approximately 5 cases per 100,000 people; however, as age increases the incidence rises to approximately 50 cases per 100,000 people age over 70 (Howlader N, 2015). Complete understanding of the pathophysiology of MDS is yet to be elucidated. However, it is generally accepted that there is an initial genetic event within a pluripotent progenitor cell followed by a sequence of inflammation with increased release of cytokines such as TNF-alpha and Interferon-gamma. This all occurs in the setting of an initial pro-apoptotic and proliferative state lending some explanation to the typically seen hypercellular marrow with peripheral cytopenias. Prognosis is predicted by cytogenetics, number of cytopenias, and blast percentage and is calculated by the International Prognostic Scoring System (IPSS) and revised IPSS (IPSS-R) (Appendix B).

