### 3. PATIENT SELECTION

#### 3.1. Eligibility criteria:

The eligibility criteria are as follows:

1. Patients must be able to understand and voluntarily sign an informed consent form.
2. Age  $\geq 18$  years at the time of signing the informed consent form.
3. Able to adhere to the study visit schedule and other protocol requirements.
4. Pathologically confirmed disease with A or B as follows:
  - A. AML patients who either have:
    - 1) Relapsed or refractory disease after receiving one or more courses of induction chemotherapy, hypomethylating agent therapy, or bone marrow transplant *or*
    - 2) *de novo* AML but not deemed to be a candidate for conventional therapy based on age, co-morbidities, or patient preference
  - B. MDS, CMML, or MDS/MPN with high risk features as defined below who have relapsed after initial response or are refractory (failure to achieve a CR, PR, or HI) after receiving at least 4 cycles of hypomethylating agents 5-azacitidine or decitabine  $\pm$  other therapies  $\pm$  bone marrow transplant OR with *de novo* MDS but have refused to receive hypomethylating therapy:
    - 1) INT-2 or high IPSS score OR high or very high IPSS-R *or*
    - 2) Secondary MDS (defined as MDS developing in a patient with an antecedent hematologic disorder or any patient with prior chemotherapy or radiation exposure) *or*
    - 3) INT-1 IPSS or intermediate R-IPSS MDS with excess blasts ( $\geq 5\%$  blasts in BM) or transfusion-dependency *or*
    - 4) MDS progressing to oligoblastic AML with 21-30% BM blasts *or*
    - 5) CMML or MDS/MPN with  $\geq 5\%$  marrow blasts, transfusion-dependency, abnormal karyotype, or proliferative features (white blood cell count  $\geq 13,000/\mu\text{L}$ , splenomegaly on physical examination, or extramedullary disease)
5. ECOG performance status of  $\leq 2$  at study entry or Karnofsky  $\geq 60\%$  (**Appendix C**).
6. Laboratory test results within these ranges:
  - ❖ Creatinine level of 3 mg/dL or lower
  - ❖ Total bilirubin  $\leq 3$  mg/dL unless due to Gilbert's syndrome, hemolysis, or ineffective hematopoiesis
  - ❖ AST (SGOT) and ALT (SGPT)  $\leq 3$  x ULN
  - ❖ WBC  $\leq 10,000/\mu\text{L}$
7. Patients must not have received any other treatment for their disease, including hematopoietic growth factors, aside from hydroxyurea for count control, within three weeks of beginning the trial, and should have recovered from all toxicities of prior therapy (to grade 0 or 1).

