**Pharmacodynamics:**

Biologic correlates include measurement of markers of myeloid differentiation by flow cytometry (e.g. CD15, CD11b), BM blast count, and ANC at the different dose levels in the dose escalation phase and at the RP2D in the expansion phase at the different time points compared to baseline. In addition, we will look at the ratio of ANC to BM blast count as clinical marker for differentiation at the different time points compared to baseline. Statistics will be descriptive and will consist of paired Student's t-tests or Wilcoxon rank sum tests comparing averages between 2 time points (e.g. after induction therapy compared to baseline).

We will furthermore assess *in vivo* changes in detectable chromosomal abnormalities in patients with baseline cytogenetic alterations that define their malignant clones. This will be measured by fluorescent in situ hybridization (FISH) with cells from the individual cellular compartments quantified as a ratio of malignant to non-malignant cells (i.e., mononuclear cells with the cytogenetic finding to those without). Successful differentiation would be expected to result in a decrease in mononuclear cells harboring the cytogenetic abnormality. These results will be summarized using descriptive statistics and exploratory plots will be used to illustrate results.

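### Section 8.1 item 3 counts clone-positive blood neutrophils as evidence of drug-induced differentiation without comparing them with the patient's own baseline

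*Combined protocol and SAP*

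**What the plan says.** Section 8.1 item 3 covers in vivo cytogenetic changes and has three parts.

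- Clinical FISH: "analysis will be done prior to starting treatment and subsequent analyses will take place with each clinical BM", to assess cytogenetic response.
- Research FISH, where possible: "FISH will additionally be used to quantify the cytogenetic changes in PB and marrow myeloid progenitors prior and following therapy on day 14" and/or after cycle 1.
- The interpretive rule: "The presence of mature neutrophils with the malignant cytogenetic abnormality in the PB will serve as evidence for terminal differentiation of leukemia cells from the" (the sentence closes by naming the study treatment).

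The rule does not require that such neutrophils be absent or fewer before dosing, and it gives no cut-off.

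Section 11.7 (Pharmacodynamics) describes the FISH analysis as a ratio of malignant to non-malignant cells, explained as "mononuclear cells with the cytogenetic finding to those without". It states the expected direction: "Successful differentiation would be expected to result in a decrease in mononuclear cells harboring the cytogenetic abnormality". Results are to be described and plotted. Neutrophil FISH is not mentioned. Section 11.3 lists changes in detectable cytogenetic abnormalities in blood and marrow as a phase I secondary endpoint.

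**The concern.** A finding can be credited to the drug only if it would be less likely without the drug. The presence of clone-positive neutrophils after dosing does not meet that standard when they may have been there before dosing. On MDS, section 2.2 says "it is generally accepted that there is an initial genetic event within a pluripotent progenitor cell", so cells maturing from that progenitor can carry the lesion untreated. Section 3.1 enrols MDS, CMML and MDS/MPN, and abnormal karyotype is one of the qualifying features for the last two.

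The study is single-arm, so the patient's own baseline is the only available comparator, and the rule does not use it. A patient unchanged from baseline could be reported as showing differentiation caused by IRX5183. Section 8.1 itself calls the assessment of biologic activity critical for interpreting clinical activity, and differentiation is one of the trial's stated hypotheses.

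**Working it through.** The plan attaches no figure to this rule (no cut-off, expected rate or sample size), so there is nothing to reproduce. The check has a textual part and an illustrative part.

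**Does another provision supply the baseline?**

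| Provision | What it offers | Does it replace the presence rule? |
|---|---|---|
| 8.1 item 3, research FISH | Before and after therapy, where possible; names blood and marrow myeloid progenitors | No; neutrophils are not named and the rule does not refer to it |
| 11.7 Pharmacodynamics | Mononuclear-cell ratio, a decrease expected | No; a different cell fraction and the opposite direction |
| 8.2 | Pre-study research blood; isolation of mononuclear cells described | No; but the baseline sample exists |
| 6 (opening text) | Foresees patients with a baseline neutrophil count of 1500 or more | No; but it shows some patients will have neutrophils to score before dosing |

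No section says that neutrophils are clone-negative at entry.

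**How often would an inert drug be credited?** The documents give none of the following, so all are assumptions:

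- q: share of FISH-informative patients with clone-positive blood neutrophils before dosing.
- e: chance that a sample is misclassified, equal in both directions and independent between samples.
- 10 FISH-informative patients.

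For an inert drug the true status does not change. Then:

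- Presence rule: flag rate = q(1 − e) + (1 − q)e, which is q when e = 0.
- Conversion rule (negative at baseline, positive on treatment): flag rate = q·e(1 − e) + (1 − q)·(1 − e)e = e(1 − e), whatever q is.
- Chance of at least one false flag among 10 = 1 − (1 − rate)^10.

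Presence rule:

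| q | Flag rate, e = 0 | Expected flags in 10 | P(at least one) | Flag rate, e = 0.05 |
|---|---|---|---|---|
| 0% | 0% | 0 | 0% | 5.0% |
| 10% | 10% | 1.0 | 65.1% | 14.0% |
| 25% | 25% | 2.5 | 94.4% | 27.5% |
| 50% | 50% | 5.0 | 99.9% | 50.0% |
| 75% | 75% | 7.5 | >99.9% | 72.5% |
| 90% | 90% | 9.0 | >99.9% | 86.0% |

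Conversion rule, any q:

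| e | Flag rate e(1 − e) | Expected flags in 10 |
|---|---|---|
| 0 | 0% | 0 |
| 0.02 | 0.02 × 0.98 = 1.96% | 0.20 |
| 0.05 | 0.05 × 0.95 = 4.75% | 0.47 |

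A cut-off matters as well. If 200 neutrophils were scored with a 1% per-cell false-positive rate (both assumed), at least one positive cell would appear with probability 1 − 0.99^200 = 0.87 in a patient with no clonal neutrophils.

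**The case against.** The strongest reply is that the sentence is interpretive text inside an item about changes. The sentence before it plans FISH before and after therapy, and its mention of blood can be read as covering whole blood as well as marrow progenitors. The endpoint in section 11.3 is also a change. Section 11 never classifies patients by neutrophil FISH, and the FISH results are only described and plotted. Other differentiation measures are compared with baseline: CD15 and CD11b by flow, the stem-cell ratio, ANC and blast count. Neutrophil processing and cut-offs may be in the Laboratory Manual, which is not among the documents.

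Much of this stands. It limits the consequence, and the silence on a cut-off does not show that the laboratory lacks one. It does not rescue the sentence: baseline data may exist, but the stated criterion is presence and it names the therapy as the cause.

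A reader might also infer more than the documents support:

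- **That the plan claims proof, or that the rule is bound to fire with an inert drug.** The plan speaks of evidence. The rule can fire, at a rate set by an unknown baseline prevalence. If q and e are both zero it never fires falsely.
- **That the problem is equally strong in AML.** Section 2.1 describes AML as involving maturation defects, so clone-positive neutrophils before dosing are less readily assumed there.
- **That enrolling CMML or MDS/MPN patients with "proliferative features (white blood cell count" of 13,000/µL or more) strengthens the case.** Item 6 of section 3.1 caps WBC at 10,000/µL at entry, so this adds little, and the argument does not need it.

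**Conclusion.** The point holds for the rule as written: it can credit the drug with a state that was there before treatment, and no other section corrects it. In the absence of assay error, the false-flag rate for an inert drug equals the baseline prevalence of clone-positive neutrophils among FISH-informative patients. The documents do not give that prevalence, so the tabulated values are ranges under assumptions, not estimates. That these cells may be present before dosing is inferred from the protocol's account of MDS and from its eligibility criteria; the documents do not report it as an observation.

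The reach is limited. A reader might take the percentages as error rates of the trial, but they are not: this is a descriptive correlative, and the primary response endpoint, the DLT rules and the Simon two-stage decision do not use it. What is at risk is the mechanistic interpretation. The correction is worth making because it is specific and cheap.

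**What to change.** Replace the presence sentence in section 8.1 item 3 with a within-patient rule along these lines:

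> Evidence of differentiation is conversion from FISH-negative to FISH-positive mature neutrophils, or a pre-specified rise from the pre-study sample in the percentage of FISH-positive mature neutrophils, beyond the laboratory's cut-off and counting error. Presence alone in a patient already positive at baseline does not count. Patients whose neutrophils are close to 100% clonal at baseline are reported as not informative for this measure.

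In section 11.7, report baseline and day-14 or post-cycle-1 neutrophil percentages as pairs, and show the change in FISH-positive mononuclear cells or progenitors alongside. Do not make a concurrent fall in blasts a condition: section 5.6 says that rising blasts may themselves reflect differentiation, so that condition could reject a true effect. The size of the required rise must come from the laboratory's assay data, since the documents contain nothing from which to set it.

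Cost: no new visit or blood draw, because section 8.2 already schedules pre-study research blood. A neutrophil preparation has to be specified if the Laboratory Manual does not already provide one, since section 8.2 describes mononuclear cells only. Baseline neutrophils must also be scored in FISH-informative patients. Fewer patients will be called positive, and some will be uninformative.

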## 8.2. **Cellular Collection and Processing:**

The labs of Drs. [name] and [name] will support the planned biologic correlatives through the timely collection and processing of the patient PB and marrow samples. All operating procedures for specimen collection, handling and storage will be standardized. Common standardized operating procedures (SOPs) will be to collect approximately 10 mL PB (1 green top tube-sodium heparin) at the time points of bone marrow assessments (i.e., pre-study, day 14  $\pm$ 3, after cycle 1, cycle 2, cycle 4, cycle 6 (and beyond as per figure 2 in section 5.1 above). Bone marrow aspirate, approximately 10 mL (1 green top tube-sodium heparin), will be collected at the above listed time points, per the protocol in figure 2. For a patient that progresses and is removed from study treatment, additional blood or BM may be obtained at the time of routine collection. Re-adjustment of the direction of bone marrow aspirate needle should take a place after the clinical collection to prevent hemodilution. At the time of collection, tubes must be thoroughly mixed to prevent clotting.

The SKCCC specimen should be delivered to the [name] and [name] laboratory immediately after collection. Specimens should be labeled with the patient's initials, study number, sample collection date and time, and sample source (PB or BM). All data should be kept in the laboratory log.

At each sampling interval, mononuclear cells from PB and marrow will be isolated per procedures in the Laboratory Manual. Samples stored in liquid nitrogen should be clearly marked with the patient's identification number (given at the time of registration), study number, sample collection date, and sample source (PB or BM).

## 9. PHARMACEUTICAL INFORMATION

A list of the adverse events and potential risks associated with the investigational or commercial agents administered in this study can be found in Section 9.2.

### 9.1. IRX5183 drug information:

#### Other Names

NRX195183

AGN195183

CNC195183

VTP195183

#### Pharmacological Classification

Retinoid, antineoplastic agent

#### Position in Class

Receptor-specific agonist (RAR $\alpha$  specific)

[figure not shown]
#### Chemical name

4-[[1-(4-Chloro-3-hydroxy-5,5,8,8-tetramethyl-5,6,7,8-tetrahydronaphthalen-2-yl)-methanoyl]-amino]-2,6-difluorobenzoic acid

#### Empirical Formula

C22H22ClF2NO4

#### Structural Formula

### Dosage Form

The drug is formulated as a soft gelatin capsule containing IRX5183 25 mg per capsule.

### Product Description

White to off-white soft gelatin oblong capsule containing a slightly hazy, yellow solution.

**Table 3: Formulation of NRX 195183 Soft Gelatin Capsules**

Ingredient	% w/w	Amount/Capsule (mg)	Function
Fill Formulation:			
NRX 195183	5	25.0	Active
Propylene Glycol USP	5	25.0	Plasticizer
Polysorbate 80 NF	90	450.0	Solubilizing Vehicle
Gel Mass for Soft Gelatin Capsules	AR*	AR	Capsule Shell

AR=As required per batch record. The following ingredients are used in the Gel Mass: Gelatin NF (150 Bloom Limed Bone, Type B), Glycerin 99.7% UPS, Sorbitol Special, 76%, Purified Water USP, Opatint White G-18000. The following processing aids are used in the capsulation process: Miglyol 812 N (Medium-Chain Triglycerides EP) and Centrocip® 162-US (Lecithin NF).

### Storage Conditions

Store refrigerated (2° - 8°C) in tight containers, protected from light.

### Excretion

Biliary and/or gastrointestinal.

### Elimination Half Life

3.3 to 16.1 hours

### Availability

IRX5183 is not commercially available. Io Therapeutics, Inc. has agreed to provide this agent for this study.

## **9.2. Side effects:**

**9.2.1. Adverse events in phase I trial in solid tumor patients:**

- 1) Dermatologic: Rash (26.7%), mucosal inflammation (6.7%), stomatitis (6.7%)
- 2) Endocrine: Hyperglycemia (26.7%), hypoglycemia (6.7%), hypertriglyceridemia (20%)
- 3) Gastrointestinal: Vomiting (33.3%), nausea (26.7%), dyspepsia (26.7%)
- 4) Hematologic Effects: Anemia (26.7%)
- 5) Hepatic: Elevated alkaline phosphatase (40%)
- 6) Other: Fatigue (40%), anorexia (26.7%)

**9.2.2. Teratogenic Effects:**

There is a high risk that a severely deformed infant will result if IRX5183 is administered during pregnancy.

If, nonetheless, it is determined that IRX 195183 represents the best available treatment for a woman of childbearing potential, it must be assured that the patient has received full information and warnings of the risk to the fetus if she were to be pregnant and of the risk of possible contraception failure and has been instructed in the need to use two reliable forms of contraception simultaneously during therapy and for 1 month following discontinuation of therapy, and has acknowledged her understanding of the need for using dual contraception, unless abstinence is the chosen method.

Within 1 week prior to the institution of IRX5183 therapy, the patient should have blood or urine collected for a serum or urine pregnancy test with a sensitivity of at least 50 mIU/mL. When possible, IRX5183 therapy should be delayed until a negative result from this test is obtained. When a delay is not possible, the patient should be placed on two reliable forms of contraception. Pregnancy testing and contraception counseling should be repeated monthly throughout the period of IRX5183 treatment.

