### 3.3. **Pregnancy:**

The effects of IRX5183 on the developing human fetus are unknown. For this reason, women of childbearing potential and men must agree to use adequate contraception (hormonal or barrier method of birth control; abstinence) prior to study entry and for the duration of study participation. Should a woman become pregnant or suspect she is pregnant while she or her partner is participating in this study, she should inform her treating physician immediately. Men treated or enrolled on this protocol must also agree to use adequate contraception prior to the study, for the duration of study participation, and 4 months after completion of IRX5183 administration.

Sexually active women of childbearing potential (WOCBP) must use an effective method of birth control during the course of the study, in a manner such that risk of failure is minimized. Before enrolling WOCBP in this clinical study, the investigator must review the guideline about study participation for WOCBP, which can be found in the GCP Manual for Investigators. The topics include the following:

- ❖ General Information
- ❖ Informed Consent Form
- ❖ Pregnancy Prevention Information Sheet
- ❖ Drug Interactions with Hormonal Contraceptives
- ❖ Contraceptives in Current Use
- ❖ Guidelines for the Follow-up of a Reported Pregnancy

Before study enrollment, WOCBP must be advised of the importance of avoiding pregnancy during study participation and the potential risk factors for an unintentional pregnancy. The subject must sign an informed consent form documenting this discussion. **All WOCBP MUST have a negative pregnancy test within 72 hours before receiving their first dose of IRX5183.** The minimum sensitivity of the pregnancy test must be 25 IU/L or equivalent units of HCG. If the pregnancy test is positive, the subject must not receive IRX5183 and must not be enrolled in the study. **In addition, all WOCBP should be instructed to contact the investigator immediately if they suspect they might be pregnant (e.g., missed or late menstrual period) at any time during study participation.**

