### 5.4. Duration of therapy:

Treatment is planned for 56 days of induction therapy (as above) and four 28-day cycles of consolidation/maintenance in patients with at least SD after induction, with an opportunity to continue on maintenance if patients remain in at least SD after 4 cycles of consolidation/maintenance (see details in section 5.1 above), or until one of the following criteria applies:

- 1) Disease progression as defined in IWG-2003 (**Appendix A1**) for AML and IWG-2006 for MDS (**Appendix A2**).
- 2) Intercurrent illness that prevents further administration of treatment or inability of the patient to continue treatment for any other reason.
- 3) Unacceptable adverse event(s) requiring temporary or permanent stopping of study drug defined in sections 5.2 and 6.
- 4) Patient decides to withdraw from the study.
- 5) General or specific changes in the patient's condition render the patient unacceptable for further treatment in the judgment of the investigator.
- 6) Pregnancy  
All WOCBP should be instructed to contact the investigator immediately if they suspect they might be pregnant (e.g., missed or late menstrual period) at any time during study participation. Institutional policy and local regulations should determine the frequency of on study pregnancy tests for WOCBP enrolled in the study.

The investigator must immediately notify Io Therapeutics in the event of a confirmed pregnancy in a patient participating in the study or partner of the patient.

7) Termination of the study by sponsor.

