## 10. STUDY CALENDAR

Baseline evaluations are to be conducted within 14 days prior to start of protocol therapy (first dose of IRX5183). In the event that the patient’s condition is deteriorating, laboratory evaluations should be repeated within 48 hours prior to initiation of therapy. An interim history and physical should be done with each visit. IRX5183 will each be administered on a daily basis with one cycle consisting of 28 days (4 weeks).

Complete blood counts with WBC differential and blood chemistries will be measured twice weekly during the first cycle of treatment, at least weekly throughout the second cycle of therapy, at least every other week during consolidation/maintenance, and at least monthly during extended maintenance, or as often as clinically indicated. Fasting lipids with triglyceride evaluation will occur q2 weeks through the first month and then q8 weeks subsequently, per standard of card assessment on retinoid therapy.

Treatments and Evaluations ▲	Pre-Study	Cycle 1:				Cycle 2:				Cycles 3-6: 				End of Study
		W1 D1&4	W2 D1&4	W3 D1&4	W4 D1&4	W1 D1	W2 D8	W3 D15	W4 D22	W1 D1	W2 D8	W3 D15	W4 D22	
IRX5183 (daily)		X	X	X	X	X	X	X	X	X	X	X	X	
Informed consent	X													
Adverse Events and Toxicity Reporting	X	X X	X X	X X	X X	X	X	X	X	X	X	X	X	X**
Medical history	X	X	X	X	X	X		X		X		X		X##
Physical exam	X	X	X	X	X	X		X		X		X		X##
Height	X													
Transfusion Review	X	X X	X X	X X	X X	X	X	X	X	X		X		
Weight	X	X		X		X		X		X		X		
ECOG Perform Status	X	X	X	X	X	X	X	X	X	X	X	X	X	
FACTleu questionnaire	X								X*				X*	
CBC w/ diff., plts	X	X X	X X	X X	X X	X	X	X	X	X		X		
Comprehensive Panel	X	X X	X X	X X	X X	X	X	X	X	X		X		
Fasting Lipid Panel 	X		X		X								X	
Urine Pregnancy	X													
JH Path Review of Diagnosis	X#		X#			X#			X#				X#	X
Peripheral Blood for Research	X#		X#			X#			X#				X#	X
Pharmacokinetics		X♦	X♦			X♦								

Bone Marrow Aspirate Biopsy 	X#		X#		X#		X#		X#	X
--	----	--	----	--	----	--	----	--	----	---

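### The pregnancy-prevention rules disagree on on-treatment testing, on starting without a negative result, and on contraception for women; the calendar schedules no on-treatment test

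*Combined protocol and SAP*

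**What the plan says.** All references are to the combined protocol and SAP.

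**On-treatment testing.** Section 9.2.2: "Pregnancy testing and contraception counseling should be repeated monthly throughout the period of IRX5183 treatment". Section 5.4: "Institutional policy and local regulations should determine the frequency of on study pregnancy tests for WOCBP enrolled in the study". In the section 10 calendar, the row labelled "Urine Pregnancy" carries a single mark, under Pre-Study. The calendar notes say who counts as a woman of childbearing potential and allow extra laboratory draws on clinical grounds. None sets a repeat schedule.

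**Before the first dose.** Section 3.3: "All WOCBP MUST have a negative pregnancy test within 72 hours before receiving their first dose of IRX5183". Section 3.1, item 9, makes the same 72-hour negative test an eligibility criterion. Section 9.2.2 has the sample taken "Within 1 week prior to the institution of IRX5183 therapy", advises waiting for a negative result if that can be done, and adds: "When a delay is not possible, the patient should be placed on two reliable forms of contraception".

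**Assay.** Section 3.3: "The minimum sensitivity of the pregnancy test must be 25 IU/L". Section 9.2.2 gives 50 mIU/mL.

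**Contraception for women.** Section 3.3 asks for an effective method (hormonal, barrier or abstinence) while the woman takes part. It gives men a further 4 months after treatment and gives women no post-treatment period. Section 9.2.2 asks for two reliable methods at once, during therapy and for 1 month afterwards, with abstinence as the exception.

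**Fetal risk.** Section 3.3 calls the effects on the human fetus unknown. Section 9.2.2 calls the risk of severe deformity high.

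**The concern.** IRX5183 is a retinoid, and Table 4 lists spontaneous abortion and birth defects among the effects of oral retinoids. Dosing is daily for six 28-day cycles. Patients with at least stable disease short of CR may continue for up to another year, and some beyond that. Repeat testing is therefore the protocol's means of finding a pregnancy that begins on treatment, other than the woman's own report of a suspected one. Section 3.3 requires permanent discontinuation once a pregnancy is found, so a later finding means longer exposure.

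Study staff who follow the calendar alone would find no on-treatment test to perform, while staff who follow 9.2.2 would test monthly. The same split arises over whether treatment may begin before a negative result is in hand, and over what a woman is told about contraception and fetal risk when she consents.

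**Working it through.** The plan states no figure to reproduce. The check sets the passages side by side, with a count of tests and a unit conversion.

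**1. On-treatment testing: three rules**

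| Source | Rule |
|---|---|
| 9.2.2 | Monthly for the whole treatment period (advisory wording) |
| 5.4 | Frequency set by local policy and regulation |
| Section 10 calendar | None on treatment; one test pre-study |

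Count, taking monthly as about once per 28-day cycle:

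- Six calendar cycles: 6 × 28 = 168 days, and 168 / 28 = 6 tests (5 to 6 if counted by calendar month).
- Full year of extended maintenance: 12 by calendar month, or 365 / 28 ≈ 13 by cycle.
- Total if monthly: 6 + 12 = 18 to 6 + 13 = 19.
- Calendar: 0 on treatment. The one pre-study test is not part of this comparison.

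The calendar's columns stop at cycles 3-6. Its footnotes do extend other procedures into extended maintenance (monthly blood tests, and marrows after cycles 10, 14 and 18), but none mentions pregnancy tests.

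**2. Starting treatment**

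| Source | Rule |
|---|---|
| 3.1 item 9; 3.3 | Negative test mandatory within 72 hours before the first dose; 3.3 bars drug and enrolment after a positive test |
| 9.2.2 | Wait for a negative result if feasible; otherwise two contraceptive methods |

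For a woman whose result is pending and whose treatment is judged urgent, 3.1 and 3.3 say no dose, whereas 9.2.2 foresees going ahead. Both cannot govern her.

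**3. Contraception for women**

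| Source | Methods | End point |
|---|---|---|
| 3.3 | An effective method, or abstinence | End of study participation; no period stated after treatment |
| 9.2.2 | Two together, unless abstinent | 1 month after stopping therapy |

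A woman using one reliable method satisfies the wording of 3.3 and does not satisfy 9.2.2.

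**4. Secondary differences**

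- Window: 72 hours in 3.1 and 3.3; 7 × 24 = 168 hours in 9.2.2; only the general 14-day baseline window (14 × 24 = 336 hours) in the calendar. A test within 72 hours meets all three.
- Sensitivity: 1 IU/L = 1 mIU/mL, so 25 against 50 mIU/mL, a factor of 2. An assay that detects 25 also meets 50.
- The reverse does not hold: a test done 5 days before dosing with a 50 mIU/mL assay meets 9.2.2 and breaches 3.3.
- Fetal risk: unknown in 3.3, high in 9.2.2. No procedure turns on this, but women are counselled on it.

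**The case against.** The best defence is that the binding text is clear and 9.2.2 is background. The 72-hour negative test is an eligibility criterion, repeated in 3.3 in mandatory terms. Section 9.2.2 sits in the pharmaceutical information and is worded as advice. Two contraceptive methods satisfy both 3.3 and 9.2.2, and 3.3 never says that one method is enough. Few participants may be of childbearing potential, since section 2.1 gives a median age of 67 at AML diagnosis.

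Much of this stands, and it rules out several stronger readings that a reader might infer:

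- *Women would be treated for over a year without a repeat test.* The documents do not show this. Section 5.4 expects on-study tests at a locally set frequency. That policy is not in the documents, so the actual frequency is unknown, not zero. The 18 to 19 tests are also a maximum: section 5.5 expects the vast majority of relapsed or refractory AML patients not to survive past 1 year.
- *Section 9.2.2 permits dosing untested women.* It does not. It still calls for a sample, and 3.1 applies to every woman enrolled. What it foresees is starting before a negative result is available.
- *The window and sensitivity figures are irreconcilable.* They are not, because one test can meet both versions.
- *Monthly testing is already mandatory.* Section 9.2.2 says it should be done; it does not say must.

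The defence does not supply an on-treatment schedule, does not remove the sentence in 9.2.2 about starting when delay is not possible, and does not give women a post-treatment period in 3.3. The age argument bears on how many women are affected, not on whether the rules agree; eligibility begins at 18.

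**Conclusion.** The concern holds on three points: on-treatment test frequency (monthly, locally set, or unscheduled), whether a negative result is mandatory before the first dose, and the number of contraceptive methods and post-treatment period for women. On the first, the gap is 0 scheduled tests against about 6 over six cycles and up to about 12 to 13 more in a full year of extended maintenance. That count assumes one test per month or per 28-day cycle and a patient who stays on treatment throughout.

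The window, sensitivity and fetal-risk wording should be harmonised but are not in themselves evidence of a safety gap. The reading of the calendar assumes that its single mark survived conversion from PDF; this is likely, because no footnote points to repeat tests either. Endpoints, sample size and analysis are unaffected.

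**What to change.** Amend sections 3.1, 3.3, 5.4, 9.2.2 and the section 10 calendar so that each states the same rule on:

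1. on-treatment test frequency, and whether the protocol or local policy sets it;
2. whether a negative result is needed before the first dose, without exception;
3. number of contraceptive methods for women and how long they continue after treatment;
4. pre-dose window and assay sensitivity;
5. the statement of fetal risk.

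Show the agreed on-treatment tests in the calendar, with a footnote covering extended maintenance and any treatment beyond it. Check that the consent discussion matches. Which rule stands on each point is for the investigators.

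The amendment itself costs protocol and calendar wording. Any added testing depends on the rule chosen and on what local policy already provides, which the documents do not state.
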